10.2 Day 7 or Day of Discharge (if earlier than 7 days)

- Directed history and physical examination, focused on signs and symptoms of congestion
- Vital signs (including O₂ saturation and weight)
- Serum Cystatin (core laboratory)
- Creatinine, BUN, and electrolytes (local laboratory)
- Blood sample for biomarkers (core laboratory)
- Urine biomarkers
- Changes in cardiovascular medications
- Assessment for serious adverse events

10.3 Day 60

Patients will receive a telephone call to assess vital status and to check for potential rehospitalizations.

10.4 6 months

Mortality data will be collected at 6 months following randomization via telephone call.

11. OUTCOME DETERMINATIONS

11.1 **Primary Endpoints**

This study will use co-primary endpoints

- **Safety:** Change in serum cystatin C from randomization to 72 hours, based on a blinded biomarker core lab assessment
- Efficacy: Cumulative urinary volume (UV; indwelling urinary catheter) at 72 hours

Rationale for Primary Endpoints:

ROSE protocol Amendment 1: March 24, 2011

Change in serum cystatin C from randomization to 72 hours was chosen as the primary safety endpoint due to the observed association between AHF therapy with diuretics and worsening renal function and the known association of worsening renal function with other adverse outcomes.

For the assessment of short term efficacy, a variety of endpoints have been utilized in prior AHF studies. These include urine volume, change in weight and patient self assessments of symptoms, typically either dyspnea or global well being (termed patient global assessment (PGA). The ROSE-AHF study will use urine volume over 72 hours as the primary endpoint for efficacy. The rationale for this choice is urine output is related to the enhancement of renal function. Change in weight and patient self assessments of symptoms using a visual analog scale (VAS) will be secondary endpoints.

11.2 Secondary Endpoints

- Change in serum creatinine from randomization to 72 hr
- Cumulative urinary sodium excretion (UNaV) at 72 hr
- Patient global well being assessment by VAS AUC over 72 hr
- Dyspnea assessment by VAS AUC over 72 hr
- Change in weight from randomization to 72 hr
- Change from randomization in blood urea nitrogen (BUN) / serum cystatin C ratio

at 72 hr

• Development of Cardio-renal syndrome: defined as increase in serum creatinine

> 0.3 mg/dl from randomization at any time point during 72 hours after

randomization

- Persistent or worsening heart failure defined as need for rescue therapy (additional IV vasoactive agent for heart failure treatment, ultrafiltration, mechanical circulatory or respiratory support) over 72 hours after randomization.
- Treatment Failure, a composite comprised of ANY ONE of the following during the 72 hours after randomization:
 - o development of cardio-renal syndrome as defined above
 - o worsening/persistent heart failure as defined above
 - Significant hypotension requiring discontinuation of study drug
 - Significant tachycardia requiring discontinuation of study drug
 - o death

11.3 Tertiary Endpoints

- Change in serum cystatin C from randomization to 24 and 48 hr
- Cumulative UV at 24 and 48 hr
- Cumulative urinary sodium excretion (UNaV) at 24 and 48 hr
- Patient global well being assessment by VAS AUC over 24 and 48 hr
- Dyspnea assessment by VAS AUC over 24 and 48 hr
- Change in serum creatinine from randomization to 24 and 48 hr
- Changes from randomization in the bivariate vector of serum cystatin C and

cumulative UV at 24 and 72 hr

For each intervention group and placebo, the change in serum cystatin C at 24 and 72 hours and UV at 24 and 72 hours for each patient will be plotted on a two dimensional coordinate grid along with estimates of the mean effect and a 95% confidence ellipse (separate plots will be produced for the 24-hour data and the 72-hour data). This graphical presentation will allow visual and statistical assessment of the "trade off" between change in serum cystatin C and UV. Comparisons will be constructed for dopamine vs. placebo and nesiritide vs. placebo to visualize the differences between treatment strategies.

• Changes from randomization in the bivariate vector of creatinine and weight at 24

and 72 hr

For each ingtervention group and placebo, weight loss at 24 and 72 hours and change in creatinine at 24 and 72 hours for each patient will be plotted on a two dimensional coordinate grid along with estimates of the mean effect and a 95% confidence ellipse. This graphical presentation will allow visual and statistical assessment of the "trade off" between change in weight and change in renal function. Comparisons between dopamine vs. placebo and nesiritide vs. placebo will be constructed as described above to visualize the differences between treatment strategies.

- Time from randomization to discharge from index hospitalization
- Total days alive and free from heart failure hospitalization during the 60 days following randomization
- Changes in circulating biomarkers from randomization to 72 hours
- Changes in Urine biomarkers from randomization to 72 hours, day 7, or discharge if earlier

• Mortality during the six months following enrollment

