9.2 Baseline Assessments

At the time of randomization, all study subjects will undergo

- Directed history and physical examination, focused on signs and symptoms of congestion
- Vital signs (including O₂ saturation and weight)
- Concomitant cardiovascular medications
- Serum Cystatin C (core laboratory)
- Serum creatinine, BUN, and electrolytes (local laboratory)
- Patient Global Well being assessment (PGA) by VAS (see Appendix C)
- Dyspnea assessment by VAS (see Appendix C)
- Blood sample for biomarkers core laboratory
- Urine Biomarkers

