10. FOLLOW UP EVALUATIONS

The 24-hour assessment should occur between 22 and 26 hours after randomization. The 48-hour assessment should occur between 46 and 50 hours after randomization. The 72-hour assessment should occur between 70 and 74 hours after randomization.

The protocol described assessments and urine collection times should be based on the randomization date and time as the anchor. Urine should be collected from randomization through 72 hours. In instances where the start of study drug is delayed 6 or more hours after randomization, an additional urine collection for assessing urinary sodium excretion is required. This urine collection would begin at the 72 hour from randomization point and end at the conclusion of the 72 hour study drug infusion point.

10.1 24, 48 and 72 hours

Between randomization and 72 hours, all study subjects will undergo the following assessments daily:

- Directed history and physical examination, focused on signs and symptoms of congestion
- Vital signs (including O₂ saturation and weight)

- Serum Cystatin C (core laboratory)
- Serum creatinine, BUN, and electrolytes (local laboratory)
- PGA assessment by VAS at 24, 48, and 72 hours
- Dyspnea assessment by VAS at 24, 48 and 72 hours
- Fluid balance between randomization and 24 hours (net intake net output), 24 and 48 hours, and 48 and 72 hours
- Blood sample for biomarkers core laboratory
- Changes in cardiovascular medications
- Assessment for serious adverse events
- Urine biomarkers
- Urine collection for UNaV

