13.4 Analysis of Secondary and Tertiary Endpoints

General linear models and nonparametric approaches will be used to analyze the continuous outcomes. For binary outcomes, logistic regression analysis will be used to compare each treatment vs. placebo and estimate the odds ratio and 95% confidence interval for low-dose dopamine vs. placebo and low-dose nesiritide vs. placebo comparisons. Time-to-event comparisons will be conducted using Kaplan-Meier curves and log-rank tests. For analyses of patient global well being VAS and dyspnea VAS, the value of zero will be imputed for all measurements missing due to death. Sensitivity analyses, including the worst-rank score analysis ⁽²¹⁾ will be employed to assess the influence of informatively missing values on the results. In particular the worst-rank score analysis will account for missing data due to deaths.

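### The VAS AUC endpoints include the score taken before treatment (half of the 24 h AUC, one sixth of the 72 h AUC, by the trapezoid rule); naming baseline VAS as a covariate is a free gain in precision

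*Protocol*

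**What the plan says.** Section 11.2 lists two VAS areas among its nine secondary endpoints: "Patient global well being assessment by VAS AUC over 72 hr" and "Dyspnea assessment by VAS AUC over 72 hr". Section 11.3 adds the shorter windows as tertiary endpoints: "Patient global well being assessment by VAS AUC over 24 and 48 hr" and "Dyspnea assessment by VAS AUC over 24 and 48 hr". These are the only patient-reported outcomes in the trial.

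The readings behind them are few. Section 9.2 places the first at randomization ("At the time of randomization, all study subjects will undergo" both scales). Section 10.1 then schedules "Dyspnea assessment by VAS at 24, 48 and 72 hours", with the same times for global well-being, and Appendix A agrees. Both instruments in Appendix C ask how the patient feels at that moment, so no reading covers the interval between visits.

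On analysis, section 13.4 says "General linear models and nonparametric approaches will be used to analyze the continuous outcomes". For the VAS it adds that readings missing because of death are set to zero, with a worst-rank sensitivity analysis. The protocol does not say how the AUC is computed or how the randomization score enters the analysis.

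**The concern.** An area over 24 h needs readings within those 24 h. Here there is one at the start, before study drug, and one at the end. The 24 h AUC is then a rescaled average of an untreated score and a single later score. Differences between patients at baseline go straight into the outcome, and they carry no information about treatment.

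A general linear model can remove that spread if V0 is a covariate. Section 13.4 neither requires nor excludes this. It also names nonparametric approaches, and a standard two-sample rank test has no covariate, so it would rank the area with the baseline spread left in. At stake is the precision of the symptom results: most at 24 h, less at 72 h.

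**Working it through.** The protocol states no effect size, SD, power or formula for the VAS endpoints, so there is no figure to reproduce.

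**Inputs.** From the protocol: reading times 0, 24, 48 and 72 h (sections 9.2 and 10.1, Appendix A); 120 patients per arm (section 5); significance at 0.05 (section 13.1, taken as two-sided). Assumed, because the protocol gives none: the trapezoid rule, equal SDs (set to 1), a common correlation ρ of 0.3, 0.5 or 0.7 between any two readings, and complete data.

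**Weights.** Time-averaged trapezoid area A, as weights on the successive readings:

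- 24 h: (1/2, 1/2), so the area itself is 12 × (V0 + V24)
- 48 h: (1/4, 1/2, 1/4)
- 72 h: (1/6, 1/3, 1/3, 1/6)

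V0 has the same expectation in every arm, so it cancels from the mean difference. A constant effect d at each later reading appears as 0.50d, 0.75d and 0.83d on the time-averaged scale. That is a choice of scale and not a bias.

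**Variance with and without V0.** With w0 the weight of V0:

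- Var(A) = ρ + (1 − ρ)Σw²
- Cov(A, V0) = w0 + ρ(1 − w0)
- Variance left after adjustment = Var(A) − Cov(A, V0)²

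Σw² is 0.5 at 24 h, 0.375 at 48 h and 10/36 = 0.278 at 72 h.

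| Window | ρ | Var(A) | Cov(A, V0) | Left after adjustment | Share left |
|---|---|---|---|---|---|
| 24 h | 0.3 | 0.650 | 0.650 | 0.2275 | 35% |
| 24 h | 0.5 | 0.750 | 0.750 | 0.1875 | 25% |
| 24 h | 0.7 | 0.850 | 0.850 | 0.1275 | 15% |
| 48 h | 0.3 | 0.5625 | 0.475 | 0.337 | 60% |
| 48 h | 0.5 | 0.6875 | 0.625 | 0.297 | 43% |
| 48 h | 0.7 | 0.8125 | 0.775 | 0.212 | 26% |
| 72 h | 0.3 | 0.494 | 0.417 | 0.321 | 65% |
| 72 h | 0.5 | 0.639 | 0.583 | 0.299 | 47% |
| 72 h | 0.7 | 0.783 | 0.750 | 0.221 | 28% |

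**24 h AUC against 24 h score.** Adjusted for V0, the area has effect d/2 and variance (1 − ρ²)/4. The 24 h score has effect d and variance 1 − ρ². Both give the standardized effect d/√(1 − ρ²), so the tests are identical and the area difference is 12 times the score difference. Unadjusted, the area's standardized effect is 0.5d/√((1 + ρ)/2) = 0.62d, 0.58d and 0.54d, against 1.00d for the 24 h score alone.

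**Illustrative power** at an assumed d of 0.4 SD, 120 per arm, two-sided 0.05, for ρ = 0.3 / 0.5 / 0.7:

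- 24 h: unadjusted AUC 48 / 43 / 39%; 24 h score alone 87%; adjusted for V0 90 / 95 / 99%
- 72 h: unadjusted AUC 96 / 90 / 83%; adjusted for V0 at least 99.5%

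**Subtraction instead of adjustment.** Subtracting V0 at 72 h gives weights (−5/6, 1/3, 1/3, 1/6) and variance (1 − ρ) × 34/36. At ρ = 0.3 this is 0.661, above the 0.494 of the raw area. With V0 as a covariate, the raw and subtracted areas give the same treatment estimate and test.

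**The case against.** The strongest reply is that the protocol fixes no AUC formula and no covariate set, that such details commonly belong in the SAP, and that a general linear model leaves room for V0. This is correct, and the silence alone would be no finding. What remains is that section 11.3 itself fixes an AUC for a window with one post-baseline reading, and that section 13.4 also names nonparametric analyses, to which a covariate in the linear model does not carry over.

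A reader might infer more, and the documents do not support it:

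- *That the AUC hides part of a symptom effect, or could itself produce a null result.* An area over 24 h and a score at 24 h are different quantities. If the effect builds up linearly, 12d is the true area difference. V0 cancels in expectation, and after adjustment the two tests are the same.
- *That half of every VAS endpoint is baseline.* Half applies only to the tertiary 24 h AUC. For the secondary 72 h endpoints the share is one sixth.
- *That leaving the VAS as an area contradicts the endpoints defined as changes from randomization.* Urine volume and urinary sodium are also cumulative from randomization, so the lists are not inconsistent.

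Also, not all of the gain comes from taking V0 out of the outcome. At 72 h and ρ = 0.5 the total gain is worth 1/0.467 = 2.14 times the patients. Dropping V0 and rescaling the other weights to (0.4, 0.4, 0.2) gives a variance of 0.5 + 0.5 × 0.36 = 0.68, which is worth (1/0.68)/(0.694/0.639) = 1.35 times. The remaining factor, 0.68/(0.68 − 0.25) = 1.58, is the ordinary benefit of a baseline covariate.

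**Conclusion.** The point holds as one of precision. On the protocol's own schedule and the usual trapezoid rule, V0 makes up 1/2, 1/4 and 1/6 of the 24, 48 and 72 h AUCs. Without adjustment, between 65% and 85% of the variance of the 24 h AUC, and between 35% and 72% at 72 h, is spread that V0 could remove. Those ranges rest on assumed equal variances and a common correlation of 0.3 to 0.7; the weights rest only on the schedule and the trapezoid rule. The 24 h AUC adds nothing to V0 and the 24 h score.

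There is no bias, and the co-primary endpoints are untouched. At 72 h the illustrative power is already 83% to 96% without adjustment, so the practical gain is largest for the tertiary 24 h endpoint. This is a free improvement to secondary and tertiary endpoints.

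**What to change.** - **Section 13.4:** name the VAS score at randomization as a covariate in the linear models for all VAS endpoints, and state the trapezoid rule there or in the SAP. Where a nonparametric analysis is used, make it a baseline-adjusted rank method, for example rank analysis of covariance.
- **Section 11.3 (and the matching lists in sections 1 and 2.3):** replace the 24 h VAS AUC, for both scales, with the 24 h score adjusted for V0. Keep the 48 h and 72 h AUCs.
- **Do not redefine the endpoints as baseline-subtracted AUCs.** Once V0 is a covariate this changes nothing in the linear model, and it conflicts with the zero assigned after death. A patient who dies with V0 = 10 would score −10 at the next reading, the same as a survivor who falls from 60 to 50. Keep the zero imputation and the worst-rank sensitivity analysis on the raw scale, where zero is the worst score on both instruments.

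The cost is wording, settled before unblinding, plus a rule for any missing baseline score. Baseline VAS is already scheduled for every patient, so no new data are needed. Nothing is lost at 24 h, since the adjusted area difference is 12 times the adjusted score difference.

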12. METHODS TO PROMOTE ADHERENCE AND MINIMIZE BIAS

12.1 Adherence

Since this study will be an inpatient study of relatively brief duration, it is not anticipated that any specific interventions will be required to promote adherence.

12.2 Blinding

For each of the two strategies (nesiritide vs. placebo and dopamine vs. placebo), the treatment assignments will be double-blinded.

PARTICIPANT SAFETY AND ADVERSE EVENTS

12.3 Institutional Review Boards

All Heart Failure Clinical Research Network sites will submit the study protocol, informed consent form, and other relevant study documents to their Institutional Review Board (IRB) for approval.

12.4 Adverse Events

12.4.1 Definitions

An Adverse Event (AE) is any sign, symptom, syndrome, or illness that occurs or worsens during the use of the test intervention (drug, biologic, or device) regardless of causality. A medical condition that is already present prior to treatment administration is not defined as an adverse event unless this medical condition worsens after the patient has been administered the test intervention. The details of these signs and symptoms will however be captured in the patient's CRF for inclusion in the database as baseline conditions. Clinically significant laboratory abnormalities (for example, abnormal ECHOs, ECGs, out of range blood parameters etc.) that occur or worsen during the use of a test intervention are also adverse events.

A Serious Adverse Event (SAE) is any adverse event that:

- Results in death
- Is life threatening
- Requires inpatient hospitalization or prolongation of hospitalization which is not specifically required by the protocol nor is it elective.
- Results in permanent impairment of a body function or permanent damage to a body structure
- Requires medical or surgical intervention to preclude permanent impairment of a body function or permanent damage to a body structure
- Additionally, important medical events that may not result in death, be life threatening, or require hospitalization may be considered SAEs when they jeopardize the patient or require medical or surgical intervention to prevent one of the serious outcomes listed above. Examples of such medical events include: allergic bronchospasm requiring intensive treatment in an emergency

room or at home, blood dyscrasias or convulsions that do not result in inpatient hospitalization, or the development of drug dependency or drug abuse. Medical and scientific judgment must be exercised when classifying events as serious.

The relationship between an adverse event and the study intervention, either surgical or medical, will be determined by the Investigator on the basis of his or her clinical judgment and the following definitions:

- Possibly Related: There is a reasonable possibility that the adverse event may have been caused by the study intervention. The temporal relationship of the adverse event to study intervention makes a causal relationship possible, and other drugs, therapeutic interventions or underlying conditions do not provide sufficient explanation for the observed event.
- Not Possibly Related: It is unlikely that the event was caused by the study intervention. The temporal relationship of the adverse event to the study intervention makes causal relationship unlikely and other drugs, therapeutic interventions or underlying conditions provide a more likely explanation for the event.

An Unexpected Adverse Event: is when the nature or severity of the event is not consistent with the applicable study intervention, expected clinical course or current product labeling.

The following adverse events are anticipated, disease related-events in patients with acute decompensated heart failure and therefore do not require reporting on the Adverse Event form of the CRF (although some may require reporting as study endpoints):

- Atrial fibrillation
- Ventricular tachycardia
- Myocardial infarction
- Acute coronary syndrome
- Electrolyte disturbance
- Acute renal failure
- Worsening heart failure

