5. BASIC STUDY DESIGN

This study is a randomized, double blind, placebo controlled, multi-center clinical trial of patients with signs and symptoms consistent with AHF within 24 hours of hospital admission. A total of approximately 360 patients will be enrolled in the trial.

Patients will be randomized to one of 3 treatment regimens (120 patients / treatment regime):

- 1. Optimal diuretic dosing + placebo
- 2. Optimal diuretic dosing + low dose dopamine
- 3. Optimal diuretic dosing + low dose nesiritide

Central venous line or PICC line or standard peripheral IV catheter placed in the antecubital fossa, depending on local hospital requirements, will be placed in the patients randomized to the Dopamine strategy group. Standard peripheral IV catheter will be placed in the patients randomized to the Nesiritide strategy group

ROSE protocol Amendment 1: March 24, 2011

TThere will be an initial open 1:1 randomization to a Nesiritide Strategy group or a Dopamine Strategy group. Patients in the Dopamine Strategy group will subsequently be randomized to low dose dopamine or placebo in a 2 to 1 blinded fashion. Likewise patients in the Nesiritide Strategy group will be randomized to low dose nesiritide or placebo in a 2 to 1 blinded fashion. All patients will receive open-label diuretic treatment.

Figure 4

For testing the primary hypotheses outlined in Section 2.1, the placebo patients will be pooled, so that patients randomized to receive dopamine will be compared with the pooled placebo group, and similarly, patients randomized to receive nesiritide will be compared to the pooled placebo group.

The study treatment regimen will be administered for *a total duration of* 72 hours, unless clinical reasons require discontinuation earlier.

The investigator may modify the diuretic dose at 24 and / or 48 hours. The primary assessment for both efficacy and safety will occur at 72 hours after randomization. **After** the primary assessment at 72 hours, all treatment will be open label at the treating physician's discretion.

The primary safety endpoint will be change in serum cystatin C from randomization to 72 hours, based on a standardized, blinded core lab assessment. The primary endpoint for efficacy will be cumulative urinary volume (UV; indwelling urinary catheter) at 72 hours.

Patients will be followed daily during hospitalization for assessment of serious adverse events.

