6. STUDY POPULATION AND ELIGIBILITY CRITERIA

6.1 Inclusion Criteria

- A diagnosis of heart failure as defined by the presence of at least 1 symptom (dyspnea, orthopnea, or edema) AND 1 sign (rales on auscultation, peripheral edema, ascites, pulmonary vascular congestion on chest radiography)
- Prior clinical diagnosis of heart failure Must be identified within 24 hours of hospital admission (24 hour clock begins when the admission orders are placed)
- Estimated GFR of \geq 15 but \leq 60 mL/min/1.73m² determined by the MDRD equation
- Male or female patient ≥18 years old
- Willingness to provide informed consent
- Ability to have a PICC or central line placed (if needed) within 12 hours of randomization and study drug infusion started
- Anticipated hospitalization of at least 72 hours

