8.3.4 Summary of the Risks and Benefits

As renal function is an important prognostic factor in patients with AHF, the patients randomized to the treatment groups may potentially benefit from the study. The risks of the study are:

- Low dose dopamine: **Common**: Chest pain, increase in blood pressure, fast or irregular heart rates, injection site reaction and hair follicles could stand erected
- Low dose nesiritide: **Common:** Low blood pressure nausea, dizziness; headache; insomnia; worsening of renal function at doses that are higher than what is used in this study. **Uncommon:** irregular heart rhythm, allergic reaction and increased risk of death
- The risks of blood drawing include bleeding at the puncture site, bruising and pain. These risks occur in a very small portion of the population. Patients with a hemoglobin < 9 g/dl will be excluded.
- The risk for PICC line placement include bruising, fainting, pain, swelling, scarring, bleeding, infection, a decrease in blood pressure, slowing of heartbeats, sweating and a feeling of weakness or lightheadedness. Uncommon risk includes infection at the site of the needle stick. These reactions generally do not cause any permanent harm. If a central line is needed, there may be additional risk of pneumothorax.
- This protocol may be hazardous to an unborn child. There is no medical information to determine whether there are significant risks to a fetus carried by a mother who is participating in this study. Therefore, female participants must be postmenopausal or have been surgically sterilized or have a serum negative pregnancy test.

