12.4.2 Recording and Reporting

The Site Investigator is responsible for monitoring the safety of patients enrolled into the study at the study sites. All SAEs will be documented in the source documents and, with the exception of the anticipated events, captured on the SAE page of the CRF. Non-serious AEs should be documented in the source documents and followed according to local standard of care.

All SAEs that result in death or are unexpected for and related to study drug (dopamine or nesiritide) must be reported on a HFN Expedited Event form and faxed to DCRI Safety Surveillance at [name].

Additionally, adverse events which meet the criteria of serious, related to study drug (dopamine or nesiritide), and unexpected for that drug, qualify for expedited reporting to the regulatory authorities. The Site Investigator will assess all SAEs occurring at his/her site and evaluate for "unexpectedness" and relationship to study drug. The Site Investigator is required to complete and submit a voluntary MedWatch Report for the events identified as serious, study drug related and unexpected at https://www.accessdata.fda.gov/scripts/medwatch/. A copy of this report should be kept at the site and also forwarded to the Data Coordinating Center.

Investigators are also responsible for promptly reporting adverse events to their reviewing IRB/EC in accordance with local requirements.

A Data and Safety Monitoring Board (DSMB) will review detailed safety data at regular intervals throughout the study.

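### The adverse-event window opens at study drug, not at randomization, so a serious harm from placing a PICC or central line before the infusion falls outside the definition

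*Protocol*

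**What the plan says.** Section 12.4.1 of the protocol sets the start of the window: "An Adverse Event (AE) is any sign, symptom, syndrome, or illness that occurs or worsens during the use of the test intervention". An exclusion follows: "A medical condition that is already present prior to treatment administration is not defined as an adverse event". It carries an exception, so that in full such a condition "is not defined as an adverse event unless this medical condition worsens after the patient has been administered the test intervention". What is excluded in this way still goes into the database, under another label: "The details of these signs and symptoms will however be captured in the patient's CRF for inclusion in the database as baseline conditions". The same section defines an SAE as an adverse event that meets a seriousness criterion, so it has no separate start.

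Vascular access is set by strategy. In the dopamine strategy, Sections 5 and 7.1 provide for "Central venous line or PICC line or standard peripheral IV catheter placed in the antecubital fossa, depending on local hospital requirements". The nesiritide strategy uses a standard peripheral catheter. Section 6.1 requires "Ability to have a PICC or central line placed (if needed) within 12 hours of randomization and study drug infusion started".

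Section 8.3.4 presents the hazards of PICC placement as risks of the study, including bleeding, infection, fainting and a fall in blood pressure. It adds: "If a central line is needed, there may be additional risk of pneumothorax".

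Section 9.2 places the baseline evaluation at randomization. Section 10.1 includes SAE assessment among the daily assessments between randomization and 72 hours. Section 5 has patients followed daily in hospital for SAEs.

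**The concern.** Some patients undergo an invasive procedure because they were randomized to the dopamine strategy. It falls in the interval between randomization and the first dose. The protocol foresees harm from it, but the adverse-event definition starts after it. A site that applies Section 12.4.1 as written would have no adverse event to report for a pneumothorax or a serious insertion bleed that came before the infusion and got no worse.

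Two things are at stake. The first is the safety record of the dopamine strategy as a whole, line included. The second is the exploratory comparison in Section 13.5 of the two placebo groups, which is meant to show whether the PICC line affects outcomes. If early line harms are not events, that comparison cannot see them.

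**Working it through.** The point rests on the wording. The only arithmetic is the allocation.

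**Order of events for a dopamine-strategy patient who needs a PICC or central line**
1. Randomization, with baseline evaluation at the same time (Section 9.2).
2. Line placement, after randomization (Sections 5, 6.1 and 7.1).
3. Start of infusion. Section 6.1 gives 12 hours from randomization, and Section 10 makes provision for a start delayed by 6 hours or more.
4. Infusion for 72 hours.

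**Section 12.4.1 applied to each case**
- Harm arises between steps 2 and 3 and does not worsen after step 3: not an adverse event, hence not an SAE. It is to be recorded as a baseline condition.
- Harm arises between steps 2 and 3 and worsens after step 3: an adverse event, through the exception.
- Harm first appears after step 3, for example a line infection that shows itself during the infusion: an adverse event under the first sentence.

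Only the first case is lost.

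**Comparison with the other sections**
- Section 10.1 has SAEs assessed from randomization. Under 12.4.1, nothing can qualify as an SAE until treatment is given. The two starting points differ by up to 12 hours.
- Section 9.2 closes the baseline evaluation at randomization. Under 12.4.1, a condition that arises later is to be entered as baseline.
- Section 12.4.1 also lists anticipated disease-related events that need no adverse-event form. Pneumothorax, bleeding, fainting and line infection are not on that list, so the timing rule is what excludes them.
- Section 12.4.2 sends SAEs to the case report form and leaves non-serious adverse events in the source documents. The loss from the SAE page therefore concerns serious harms only.

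**Patients who could be exposed**
- Dopamine strategy: 360 × 1/2 = 180.
- Of these, on dopamine: 180 × 2/3 = 120. On placebo: 180 × 1/3 = 60.
- Nesiritide-strategy placebo: 180 × 1/3 = 60. Pooled placebo: 60 + 60 = 120.

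So 180 is a ceiling, reached only if no hospital accepts a peripheral catheter. The protocol gives no share with a PICC or central line and no complication rate, so no event count can be derived.

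**Why the comparator matters once these events are counted**
Let r be the rate of harm specific to this access in the dopamine strategy, with none in the nesiritide strategy and no drug effect. The dopamine arm has rate r. Pooled placebo has (60 × r + 60 × 0) / 120 = r/2. Set against pooled placebo, dopamine would show twice the rate with no drug effect at all. Set against the 60 placebo patients of its own strategy, the expected rates are equal.

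**The case against.** The best defence is that the protocol, taken as a whole, does collect these events. SAE assessment runs daily from randomization. The adverse-event definition mentions devices, and relatedness is judged against a study intervention that may be surgical. Vascular access is described in Section 7.1, under the heading of treatment interventions. On that reading the line belongs to the intervention and the window opens when it is placed. The reading is possible, but nothing states it. Section 12.4.1 ties the exclusion to treatment administration, and Section 12.4.2 has the investigator judge relationship to study drug, meaning dopamine or nesiritide. If the broad reading was intended, Section 12.4.1 has to say so. What stands of this defence is that misfiling is the literal result of the text and not certain practice.

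A reader might also infer more than the documents support:
- **That all line harms, infection included, are lost.** The exception for worsening and the first sentence of 12.4.1 keep anything that progresses or first appears during the infusion.
- **That every dopamine-strategy patient faces these risks.** A PICC or central line is placed only if needed, and pneumothorax is named only for a central line.
- **That the drug comparison is biased.** Harm before the infusion cannot come from dopamine. By randomization it falls alike, in expectation, on dopamine and on placebo within that strategy, so omitting it does not distort that contrast.
- **That expedited reporting is deficient.** That route is for deaths and for unexpected, drug-related SAEs. Other SAEs still have the SAE page, the review boards and the DSMB.
- **That safety events will be compared with pooled placebo.** Pooling is stated for the primary comparisons only.

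**Conclusion.** The point holds in a narrow form. Section 12.4.1, read literally, excludes a serious insertion harm that precedes the infusion and does not later worsen. That rule contradicts SAE assessment from randomization in Section 10.1 and baseline evaluation at randomization in Section 9.2. It also takes early line harms out of the Section 13.5 placebo comparison, so far as that comparison looks at safety events.

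The exposed group is at most 180 of 360 patients (120 dopamine, 60 placebo), over an interval of up to 12 hours. The number of events is unknown and may be very small. The conclusion assumes that the line is placed for the trial, after randomization and before the infusion, and that sites apply the definition as written. It does not touch the primary endpoints. It should be corrected because the harm is foreseen, serious when it occurs, and easy to capture.

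**What to change.** - Reconcile Section 12.4.1 with Sections 5, 9.2 and 10.1 by starting the adverse-event and SAE window at randomization. Conditions present before randomization are baseline; anything new or worse afterwards is an event.
- Add study-required vascular access as a relatedness option on the SAE page, beside study drug, and refer to it in Sections 12.4.1 and 12.4.2.
- Tabulate access-related SAEs by strategy. For these events, compare dopamine with the placebo patients of the dopamine strategy and not with pooled placebo.

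The cost is a short amendment to the wording, one extra choice on an existing page and a few more SAE pages. No visit, treatment or sample-size change follows.
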